#### 6.3.2. BCVA

BCVA will be assessed per standard practice at the Screening/Baseline visit (Day 1) and at Visit 3 (and at unscheduled and early exit visits, as necessary).

For each eye, the distance visual acuity (VA) will be collected as per the site's standard of care practice using charts validated for the specific testing distance, which may include for example, 6 m for Snellen chart, 20 ft for Snellen chart, decimal chart and logMAR score. The values for BCVA will be presented in logMAR. BCVA will be summarized as a continuous variable at each analysis visit (Baseline and Visit 3) [eye-level summary]. The mean BCVA score will be presented together with the corresponding 95% CI. In addition, the change from Baseline will be summarized at Visit 3.

A supportive listing for BCVA assessments will be provided.

#### Derivations:

- BCVA (logMAR) = -log10 (20 / Snellen VA 20 ft fractions) if measured in 20 ft for Snellen chart.
- BCVA (logMAR) = -log10 (6 / Snellen VA 6 m fractions) if measured in 6 m for Snellen chart.
- BCVA (logMAR) = -log10 (decimal acuity) if measured in decimal chart.

#### **6.3.3.** Biomicroscopy Findings

Slit lamp biomicroscopy assessments will be performed using the ISO11980 grading at the Screening/Baseline visit (Day 1) and at Visit 3 (and at unscheduled and early exit visits, as necessary).

Biomicroscopy parameters will be summarized [eye-level summary]as a categorical variable by analysis visit:

- Limbal Hyperemia: None, Trace, Mild, Moderate, and Severe
- Bulbar Hyperemia: None, Trace, Mild, Moderate, and Severe
- Corneal Epithelial Edema: None, Trace, Mild, Moderate, and Severe
- Corneal Staining: Absent and Present
  - o Central: None, Trace, Mild, Moderate, and Severe
  - o Superior: None, Trace, Mild, Moderate, and Severe
  - o Nasal: None, Trace, Mild, Moderate, and Severe
  - o Inferior: None, Trace, Mild, Moderate, and Severe
  - Temporal: None, Trace, Mild, Moderate, and Severe
- Conjunctival Staining: None, Trace, Mild, Moderate, and Severe
- Palpebral Conjunctival Observations: None, Trace, Mild, Moderate, and Severe
- Other Findings: None, Trace, Mild, Moderate, and Severe

Shift tables will be generated using the ISO 11980 grading categories. The number and percentage of eyes shifting from categories between Baseline and Visit 3 will be summarized.

A supportive listing for biomicroscopy assessments will be provided.

#### 6.3.4. Device Deficiencies

Device deficiencies will be collected at the time points specified in Table 1. The number of device deficiencies reported during the study will be tabulated.

A supportive listing will be provided.

#### 6.4. Other Safety Endpoints

Not Applicable.

## 7. Analysis Strategy for Other Endpoints

#### 7.1.1. Pregnancy

Information on pregnancy during the study will be listed for female subjects with childbearing potential or female subjects who become pregnant during the course of the study. Abnormal

pregnancy outcomes (e.g., spontaneous abortion, fetal death, stillbirth, congenital anomalies, ectopic pregnancy) are considered SAEs.

## 8. Sample Size and Power Calculations

The study will recruit 68 subjects with a target to complete 54 evaluable subjects.

With a sample size of 54, a two-sided 95% CI for a single proportion will extend 0.060 from the observed proportion when the expected proportion is 0.0543 (AEs). Table 3 presents the precision for various rates of categorical outcomes.

Table 3: Precision for Various Percentages

Sample Size	Pro	ecision (%) for V	arious Rates of Outo		
Sample Size	5%	10%	25%	50%	
54	5.81%	8.00%	11.55%	13.34%	

Precision calculated according to a simple asymptotic formula for a 2-sided 95% CI for a proportion based on the normal approximation of the binomial distribution.

Investigators will be asked to enroll approximately 22% of subjects with aqueous deficient DE, 45% of subjects with evaporative DE, and 33% of subjects with mixed DE as per the Tear Film and Ocular Surface Society (TFOS) Dry Eye Workshop (DEWS) criteria.

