#### 6.4.1 Sample Size

The study will recruit 68 subjects with a target to complete 54 evaluable subjects.

With a sample size of 54, a two-sided 95% confidence interval for a single proportion will extend 0.060 from the observed proportion when the expected proportion is 0.0543 (AEs).

Table 2 presents the precision for various rates of categorical outcomes.

**Table 2.** Precision for Various Percentages

Comple Size	Precision (%) for Various Rates of Outcomes				
Sample Size	5%	10%	25%	50%	
54	5.81%	8.00%	11.55%	13.34%	

Precision calculated according to a simple asymptotic formula for a 2-sided 95% confidence interval for a proportion based on the normal approximation of the binomial distribution.

Investigators will be asked to enroll approximately 22% of subjects with aqueous deficient dry eye, 45% of subjects with evaporative dry eye, and 33% of subjects with mixed dry eye as per the TFOS DEWS II criteria.

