#### 2.1. Full Analysis Set (FAS)

The FAS will include all subjects/eyes exposed to at least one dose of Systane Complete PF. The FAS will be the primary analysis set for all effectiveness and safety analyses.

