# 3. General Aspects for Statistical Analysis

#### 3.1. General Methods

In general, summaries will present data overall and by DED groups (aqueous deficient DE, evaporative DE, and mixed DE).

No hypothesis testing will be performed. Whenever applicable, 95% confidence intervals (CIs) will be provided. For proportions, 95% CIs will be calculated using the exact Binomial (Clopper-Pearson) method [1]. 95% CIs of a normal distribution for means will be provided, as needed.

All relevant subject data will be included in listings. The listings will be sorted by subject ID, and other characteristics (age, sex, eye(s), etc.), if necessary.

Data collected for IDEEL-SB, BCVA, and Biomicroscopy findings at unscheduled visits may be included in by-visit summaries and analyzed in the same fashion as the data collected at scheduled visits except where otherwise noted.

SAS® version 9.4 or higher will be used for all statistical analyses and tabulations.

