# 6.3. Statistical Methods for Safety Analyses

The FAS will be used for all safety analyses. All safety endpoints will be summarized descriptively overall and by DED groups.

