#### 6.3.1. Adverse Events

The applicable definition of an AE is in the study protocol. All AEs will be collected from the time of signed IC until study participation is complete. AEs will be coded using the most current available version of the Medical Dictionary for Regulatory Activities (MedDRA) at the time of the data-cut.

All analyses described will be based on treatment-emergent adverse events (TEAEs), if not otherwise specified. TEAEs are those events with onset dates occurring on or after the first dose of study treatment until the end of the study. AEs with an onset date missing will be considered as TEAE.

- **AEs related with study device**: AEs recorded on the AE eCRF page, Relationship to Study Device = Related) and those of unknown relationship (i.e., no answer to the question "Relationship to Study Device").
- **AEs related with test procedure**: AEs recorded on the AE eCRF page, Relationship to Test Procedure = Related) and those of unknown relationship (i.e., no answer to the question "Relationship to Test Procedure").
- Serious adverse events (SAEs): AEs recorded on the AE eCRF page, Was this a Serious Adverse Event? = Yes.
- AEs resulting in study device permanent discontinuation: AEs recorded on the AE
  eCRF page, Action Taken Due To Adverse Event = Study Device Permanently
  Discontinued.
- AEs resulting in death: AEs recorded on the AE eCRF page, Death = Yes or Outcome
   = Fatal.
- Ocular AEs: AEs recorded on the AE eCRF page, Eye = OD or OS.

TEAEs will be summarized as the number and percentage of subjects/eyes by MedDRA Preferred Terms (PT) as an event category. Each subject/eye will be counted only once within a given PT. TEAEs will be displayed in terms of frequency tables sorted on decreasing frequency of PT. In case of equal frequency regarding PT, alphabetical order will be used. In

case any specific TEAE does not have MedDRA PT coded term, it will be summarized under the "Uncoded" category.

The following tables will be created for non-ocular TEAEs (subject-level summary):

- The overall summary table of non-ocular TEAEs will include the number of non-ocular TEAEs and the frequency (number and percentage), and the corresponding 95% CI of subjects with:
  - o Any non-ocular TEAE
  - Any moderate non-ocular TEAE
  - o Any severe non-ocular TEAE
  - Any non-ocular TEAE related with study device
  - Any non-ocular TEAE related with test procedure
  - Any serious non-ocular TEAE

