  - O Any serious non-ocular TEAE related with study device
  - o Any serious non-ocular TEAE related with test procedure
  - o Any non-ocular TEAE resulting in study device permanent discontinuation
  - o Any non-ocular TEAE resulting in death
- Non-ocular TEAEs by PT
- Serious non-ocular TEAEs by PT
- Non-ocular TEAEs related with study device by PT

For ocular TEAEs, the following data will be summarized (eye-level summary):

- The overall summary table of ocular TEAEs will include the number of ocular TEAEs and the frequency (number and percentage), and the corresponding 95% CI of eyes with:
  - Any ocular TEAE
  - Any moderate ocular TEAE
  - o Any severe ocular TEAE
  - o Any ocular TEAE related with study device
  - Any ocular TEAE related with test procedure
  - o Any serious ocular TEAE
  - o Any serious ocular TEAE related with study device
  - o Any serious ocular TEAE related with test procedure

- o Any ocular TEAE resulting in study device permanent discontinuation
- o Any ocular TEAE resulting in death
- Ocular TEAEs by PT
- Serious ocular TEAEs by PT
- Ocular TEAEs related with study device by PT

Supportive listings will be provided for all TEAEs. Ocular TEAEs will be flagged.

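### The AE precision that supports N (0.060 each side at 5.43%, n = 54) is a Wald figure, but the SAP will report Clopper-Pearson intervals, which reach about 0.043 below and 0.098 above

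*SAP*

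**What the plan says.** - **Planned precision.** SAP section 8 states, for a sample size of 54, that "a two-sided 95% CI for a single proportion will extend 0.060 from the observed proportion when the expected proportion is 0.0543 (AEs"). Table 3 adds 5.81, 8.00, 11.55 and 13.34 percentage points at rates of 5%, 10%, 25% and 50%. Its footnote gives the method: "Precision calculated according to a simple asymptotic formula for a 2-sided 95% CI for a proportion". Protocol section 6.4.1 and its Table 2 carry the same figures and the same method ("Precision calculated according to a simple asymptotic formula for a 2-sided 95% confidence interval for a proportion").
- **Planned analysis.** SAP section 3.1: "For proportions, 95% CIs will be calculated using the exact Binomial (Clopper-Pearson) method".
- **Where the intervals appear.** In SAP section 6.3.1 the overall table of non-ocular TEAEs gives "the frequency (number and percentage), and the corresponding 95% CI of subjects with" each type of event. Ocular events are handled separately: "For ocular TEAEs, the following data will be summarized (eye-level summary"), also with 95% intervals.
- **Denominator.** SAP section 6.3: "The FAS will be used for all safety analyses". SAP section 2.1: "The FAS will include all subjects/eyes exposed to at least one dose of Systane Complete PF". The 54 in section 8 is the target number of evaluable subjects out of 68 recruited.

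**The concern.** The sentence in section 8 predicts how wide the AE interval will be, but it uses a method that the same SAP does not use for its reported intervals. Near 5% with 54 subjects the choice of method matters. The Wald interval is symmetric by construction, while the exact interval is strongly skewed towards higher rates. A reader of section 8 would expect an upper limit near 11.5% at the expected AE rate, and the planned analysis would give one near 15.2%. For an adverse event rate the upper limit carries most of the information.

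The plan tests no hypothesis and has no power calculation, so this statement and its table are all that supports N numerically. Two further gaps bear on the same sentence: AEs are analysed in a set whose size is not stated, and the documents do not say whether 0.0543 is a rate per subject or per eye.

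**Working it through.** **Inputs.** n = 54, expected proportion p = 0.0543, two-sided 95% (SAP section 8); exact method (SAP section 3.1); 68 recruited (SAP section 8).

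**1. Reproduce the stated figures.** Wald half-width = 1.96 × √(p(1 − p)/n).

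At p = 0.0543: 1.96 × √(0.0543 × 0.9457 / 54) = 0.0604, which rounds to the stated 0.060. At 5%, 10%, 25% and 50% the formula gives 0.0581, 0.0800, 0.1155 and 0.1334, which match Table 3. At p = 0.0543 a continuity-corrected Wald interval (0.0697), Wilson (half-width 0.0655) and Clopper-Pearson (half-width 0.0705) do not give 0.060.

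**2. Check the lower side.** 0.0543 − 0.0604 = −0.006, and 0.05 − 0.0581 = −0.008. Both Wald lower limits are negative, so the full stated distance below the estimate is not possible for a proportion.

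**3. Apply the SAP's own method.** With x events, the lower limit is the 2.5% quantile of Beta(x, n − x + 1) and the upper limit is the 97.5% quantile of Beta(x + 1, n − x). The expected count is 0.0543 × 54 = 2.93, so the first row is an interpolation; the second is the nearest count that can occur.

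| Case, n = 54 | Exact 95% interval | Below | Above | Half-width |
|---|---|---|---|---|
| p = 0.0543 (x = 2.93) | 1.1% to 15.2% | 0.043 | 0.098 | 0.071 |
| 3/54 = 5.6% | 1.2% to 15.4% | 0.044 | 0.098 | 0.071 |

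The upper arm is 0.098 / 0.060 = 1.6 times the stated figure. Total width is 0.141, against 2 × 0.0604 = 0.121, about 17% more. Averaged over Binomial(54, 0.0543), the exact half-width is 0.068 and the upper arm 0.096.

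**4. Does it depend on the observed count?** Exact upper arm at n = 54:

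| Events | 0 | 1 | 2 | 3 | 4 | 5 | 6 | 7 | 8 |
|---|---|---|---|---|---|---|---|---|---|
| Upper arm | 0.066 | 0.080 | 0.090 | 0.098 | 0.105 | 0.110 | 0.115 | 0.119 | 0.123 |

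Counts 0 to 8 hold over 99% of the probability at 5.43%. None gives an upper arm as small as 0.060.

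**5. Denominator.** The FAS size is not given. It is at most 68 if no more than the 68 recruited subjects are dosed. At n = 68 and p = 0.0543 the exact interval is 1.4% to 13.8%: 0.040 below, 0.083 above, half-width 0.062. Averaged over the binomial, the half-width is 0.060 and the upper arm 0.082.

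**6. Other rates in Table 3** (n = 54, percentage points; exact values at 5%, 10% and 25% are interpolated).

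| Rate | Stated, each side | Exact below | Exact above |
|---|---|---|---|
| 5% | 5.81 | 4.1 | 9.6 |
| 10% | 8.00 | 6.5 | 11.2 |
| 25% | 11.55 | 10.8 | 13.7 |
| 50% | 13.34 | 13.9 | 13.9 |

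The upper-side gap is largest at the low rates, where the headline AE statement sits.

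**The case against.** The strongest reply is that nothing was miscalculated or hidden. The footnotes name the asymptotic formula, every figure reproduces, and a normal-approximation half-width is a common planning convention. The reported intervals will be valid exact intervals whatever section 8 says. All of that is true, and it limits the weight of the point. It does not make 0.060 the precision of the interval that will be reported.

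A second reply is that the FAS will probably exceed 54. At 68 the average exact half-width is 0.060, so the shortfall in total width could disappear. This stands for total width, but not for the upper arm, which is still about 0.083.

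A third reply is that the ocular TEAE tables count eyes. Assuming two eyes per subject, 108 to 136 eyes at 5.43% give an exact upper arm of 0.061 to 0.053 and a half-width of 0.048 to 0.042, so those printed intervals would not be wider than stated. The arithmetic is right, but it treats the two eyes of a subject as independent. It also shows that the finding applies to subject-level proportions only and that the scope of section 8 should be stated.

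Finally, the protocol names no interval method for AEs, so its Table 2 does not contradict the protocol itself. That is correct; the conflict is within the SAP, and the protocol edit is only for alignment.

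**Conclusion.** The inconsistency is real and the SAP statement should be corrected. For subject-level proportions near 5.43% with 54 subjects, the planned method gives about 0.043 below and 0.098 above, not 0.060 each side. The upper side is understated at every plausible count, and at a denominator of 68 it is still 0.083.

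This rests on three assumptions: 0.0543 is a per-subject rate, Clopper-Pearson is applied as SAP section 3.1 states, and the FAS lies between 54 and 68. The effect is confined to the stated precision. N, the analyses and the reporting rules are unaffected. The correction is still worth making, because no other quantitative argument for N is given.

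**What to change.** In SAP section 8, replace the 0.060 sentence and Table 3 with Clopper-Pearson limits at attainable counts:

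| Count | Rate | Exact 95% interval | Below / above (points) |
|---|---|---|---|
| 3/54 | 5.6% | 1.2% to 15.4% | 4.4 / 9.8 |
| 5/54 | 9.3% | 3.1% to 20.3% | 6.2 / 11.0 |
| 14/54 | 25.9% | 15.0% to 39.7% | 11.0 / 13.7 |
| 27/54 | 50.0% | 36.1% to 63.9% | 13.9 / 13.9 |
| 4/68 (maximum FAS, if all 68 recruited subjects are dosed) | 5.9% | 1.6% to 14.4% | 4.3 / 8.5 |

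If the 5%, 10% and 25% columns are kept, note that they correspond to 2.7, 5.4 and 13.5 subjects of 54, so exact values there are interpolated. Add a scope note saying whether 0.0543 is per subject or per eye, and that the figures apply to subject-level proportions and not to the eye-level ocular TEAE tables.

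The cost is one sentence, one table and one note in the SAP. The stated precision will look somewhat less favourable. Protocol section 6.4.1 and Table 2 can be aligned at the next amendment, since protocol changes need IRB/IEC approval (Protocol section 12). N and the analysis stay as they are.

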# 9. Quality Control and Version Control

The Statistical Analyst will direct the project team to apply quality control and data validation programming to ensure consistency and accuracy of the statistical analysis datasets, statistical analyses, and associated output, according to ICON standard operating procedures

The review

involves, but is not limited to the following: generation of QC statistics, checking calculations of derived variables, confirmation of analytic cohort, examination of the SAS® LOG or equivalent, confirmation of statistical validity, and consistency of output across tables, listings, and figures.

ICON plc will designate the initial version of the SAP approved by the Sponsor and ICON plc as Version 1.0. ICON plc will document any changes made to the SAP in a new version and the version number updated. ICON plc may complete revisions to SAP attachments without requiring additional revisions and approval to the SAP.

# 11. Revision History

This is the original (Version 1.0) Statistical Analysis Plan for this study. This version of the Statistical Analysis Plan is based on Version 1.0 of the study protocol.

# 12. Appendix

# 12.1. Handling of Partial Dates

Incomplete AE onset date will be imputed as follows:

- If the AE onset date is completely missing, then no imputation will be performed, and the AE will be considered as TEAE.
- If the day of the AE onset date is missing, but the month and year are equal to the start date of study treatment, then the AE onset day will be replaced by the day of the start date of study treatment.
- If both the day and month of the AE onset date are missing but the onset year is equal to the year of study treatment start date, then the AE onset month and day will be replaced by the month and day of study treatment start date.
- In all other cases, the missing AE onset day or missing AE onset month will be replaced by 1.

Incomplete AE end date will be imputed as follows:

- If the AE end date is completely missing and the AE is not ongoing, then the AE end date will be replaced by the end of study date. If the end of study date is missing, then AE end date will not be imputed.
- If only the day of the AE end date is missing, then AE end day will be replaced by the last day of the month, if not resulting in a date later than the end of study date.
- If both the day and month of the AE end date are missing, then no imputation will be performed.

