#### 7.3.4.1 Adverse Events

All AEs and SAEs will be collected at the time points specified in Table 4 from the time of informed consent completion until study participation is complete. Any preexisting medical conditions or signs/symptoms present in a subject prior to obtaining informed consent are not considered AEs in the study and should be recorded in the Medical History section of the eCRF. See Section 9.2 and 9.3 for further details.

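### SAP 12.1 sets a missing AE onset month to January even when day and year are known, so an on-treatment AE recorded that way can be dated before the first dose and lost from the TEAE outputs

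*SAP*

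**What the plan says.** SAP 12.1 gives four rules for an incomplete AE onset date.

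1. Nothing known: "If the AE onset date is completely missing, then no imputation will be performed, and the AE will be considered as TEAE".
2. Day missing, in the month and year of first dose: "If the day of the AE onset date is missing, but the month and year are equal to the start date of study treatment", the day of first dose is used.
3. "If both the day and month of the AE onset date are missing" and the year is that of first dose: the first-dose day and month are used.
4. Everything else: "In all other cases, the missing AE onset day or missing AE onset month will be replaced by 1".

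SAP 6.3.1 defines the events that count: "TEAEs are those events with onset dates occurring on or after the first dose of study treatment until the end of the study". It adds that "AEs with an onset date missing will be considered as TEAE", and sets the scope of the tables: "All analyses described will be based on treatment-emergent adverse events (TEAEs), if not otherwise specified". The AE listing promised in that section, and the only AE listing in the SAP 13 output list (16.2.5.1), are also confined to TEAEs.

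Protocol 7.3.4.1 collects AEs "from the time of informed consent completion until study participation is complete". Under Protocol 6.1 and Table 4, consent, eligibility and the first on-site drop all belong to the Day 1 visit.

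**The concern.** Rules 1 to 3 share one aim: when the date cannot settle the matter, keep the event as treatment-emergent. Rule 4 departs from that aim for one pattern, day and year known with month missing. There, knowing more about the date makes the event less likely to be counted.

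The imputed date can also be impossible. AEs are recorded only from consent, and consent and first drop share a visit, so a subject first dosed in mid-year cannot have a study AE that began in January of that year.

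Safety is half of the study objective, and the sample size is justified by the precision of an AE proportion. A rule that can silently drop an AE is worth closing even if it seldom fires.

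**Working it through.** **The plan's own AE figure.** SAP 8 and Protocol 6.4.1 give n = 54, expected AE proportion 0.0543 and half-width 0.060. Normal approximation: 1.96 × √(0.0543 × 0.9457 / 54) = 0.0604, which reproduces it. The date rule has no stated figure of its own.

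**One event, four ways of recording it.** Assumed dates: first dose 10 July 2023, true onset 20 July 2023.

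| Known parts | Rule | Imputed onset | TEAE? |
|---|---|---|---|
| none | 1 | none | yes |
| year | 3 | 10 July 2023 | yes |
| month, year | 2 | 10 July 2023 | yes |
| day, year | 4 | 20 January 2023 | no |

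The imputed date in the last row is also earlier than the protocol date of 24 April 2023.

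**How often the pattern loses an event, by month of first dose.** The four rules were applied literally to every onset on study days 1 to 32 (the end of the Visit 3 window), for every first-dose date in an assumed range, each combination weighted equally. An event is lost if its imputed date is before first dose.

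| Assumed first dose | Month-missing onsets lost |
|---|---|
| 25 Apr to 30 Nov 2023 | 7,040 / 7,040 (100%) |
| 1 Feb to 29 Nov 2024 | 9,696 / 9,696 (100%) |
| December 2023 | 496 / 992 (50%) |
| January 2024 | 467 / 992 (47%) |
| any day in 12 months from 25 Apr 2023 | 10,691 / 11,712 (91%) |

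The pattern is easy to see by reasoning:

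- *February to November.* Day 32 falls no later than 31 December, so onset and first dose share a year. The imputed date is no later than 31 January, so it always precedes first dose.
- *December, first dose on day d.* The 32 − d onsets still in December are lost. Summed over d = 1 to 31 this is 31 × 32 / 2 = 496. Onsets in the following January are dated correctly.
- *January.* January onsets are dated correctly. Later onsets whose day of the month is before the first-dose day are lost.

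With the day missing, or day and month both missing, no event was lost in any of these ranges. The gap is confined to this one pattern.

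**Scale.** Expected subjects with an AE: 0.0543 × 54 = 2.9; 0.0543 × 68 = 3.7. Suppose, as an assumption, one AE per such subject and 0.1% to 2% of onset dates with day and year but no month. The expected number of affected events is then 3 × 0.001 = 0.003 to 4 × 0.02 = 0.08.

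**The case against.** The strongest reply is that the branch is hardly reachable. Follow-up is about 30 days with three contacts, AEs are asked about at each visit (Protocol 9.2), an occurrence date is required for ADEs and SAEs (Protocol 9.3), and missing data must be explained (Protocol 10.3). A site would have to know day and year but not month, and nothing shows that the eCRF accepts such a date. This stands, and it makes the point minor. It does not make the rule right.

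A second reply is that SAP 6.3.1 already counts an AE with a missing onset date as treatment-emergent. SAP 12.1 narrows that to a completely missing date and gives partial dates their own rules, so the sentence does not clearly rescue the event. Nor does the general statement in SAP 3.1 that relevant data will be listed, because no listing of other AEs is planned. The checks on derived variables in SAP 9 might catch an impossible date, but would leave no rule for correcting it.

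Three stronger readings are tempting, and the documents do not support them:

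- *The event vanishes from the report.* It may still appear as a reason for discontinuation (SAP 4.1), and SAEs and ADEs reach the sponsor separately under Protocol 9.3.
- *The AE rules favour the product.* Only this sub-case does, for on-treatment events. The other onset rules lean the other way, and SAP 6.3.1 counts an AE with no recorded relationship as related.
- *The reported rate would fall from 3/54 to 2/54.* No planned table shows that proportion. Safety uses the FAS, which lies between 54 and 68 subjects if targets are met. Non-ocular events are counted by subject and ocular events by eye (up to 2 × 68 = 136). The figure also assumes that the lost AE was the subject's only one.

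**Conclusion.** The rule as written gives a wrong result for one date pattern: an on-treatment AE with day and year known but month missing can be placed before first dose and so leave the TEAE tables and the only AE listing. This is certain for first doses from February to November and occurs in about half of cases for December or January.

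The conclusion rests on two things that the documents do not settle: that the eCRF permits the pattern, and when subjects are dosed. The expected effect is small, well below one event under the assumed frequencies. The point is a minor correction, worth making because only about 3 to 4 subjects with an AE are expected and a single lost event would matter against that count.

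**What to change.** Add to the last onset bullet of SAP 12.1:

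> *If the known parts of the date do not place the onset before the first dose, the AE is a TEAE; if the imputed date would fall before the first dose, use the earliest date on or after the first dose that agrees with the known parts.*

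For programming, the known parts place the onset before first dose when no calendar date on or after first dose agrees with them. In the worked example the onset becomes 20 July 2023, so the recorded day is kept. No on-treatment event can then be lost: its true date is on or after first dose and agrees with the known parts, so a qualifying date always exists.

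The cost is one sentence and one more line of programming. An AE arising between consent and first drop could be counted as a TEAE. Both belong to the same visit, and a comparison by date alone would already count such an AE if they fall on one day. The reference in SAP 3.4, which sends the reader to Appendix 13.1 for these rules, can be corrected to 12.1 in the same edit. If the eCRF rejects a date with day and year but no month, saying so in SAP 12.1 would also close the gap.
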